## **8.4. Endpoints**

### **8.4.1. Primary Endpoint**

The primary endpoint is the proportion of patients who have at least a partial response to treatment. A partial response or better will be considered synonymous with “success”, unless specified otherwise. The 6 patients treated at the recommended dose level (MTD) within each group will be included in the analysis for this portion of the study. The efficacy population will include the 63 patients across groups and include all patients meeting eligibility criteria who signed a consent form and began treatment.

### **8.4.2. Secondary Endpoints**

In this section:

- Survival time is defined as the time from registration to death due to any cause.
- Progression-free survival time is defined as the time from registration to the earliest date of documentation of disease progression. If a patient dies without a documentation of disease progression the patient will be considered to have had disease progression at the time of their death. If the patient is declared to be a major treatment violation, the patient will be censored on the date the treatment violation was declared to have occurred. In the case of a patient starting treatment and then never returning for any evaluations, the patient will be censored for progression on day 1 post-registration.
- Duration of response is defined for all eligible, treated patients who have achieved a partial response or better as the date at which the patient’s earliest objective status is first noted to be either a partial response or better to the earliest date progression is documented.
- Time to treatment failure is defined to be the time from registration to the date at which the patient is removed from treatment due to progression, adverse events, or refusal. If the patient is considered to be a major treatment violation or is taken off study as a nonprotocol failure, the patient will be censored on the date they are removed from treatment.

The failure time distributions for the secondary endpoints defined above will be estimated using Kaplan-Meier methods.

## **8.5. Analysis Populations**

This section is designed to identify the characteristics that are necessary for inclusion in particular populations defined for the purpose of analysis.

### **8.5.1. Intent-to-Treat (ITT) Population**

The intention-to-treat (ITT) population is defined to include all patients as randomized.

### **8.5.2. Safety Population**

The safety population is defined as all patients treated with at least one dose of trial therapy. All safety data collected up to the end of the study (i.e., through the last follow-up evaluation) are included in the safety analysis.

### **8.5.3. Efficacy Population**

The efficacy population is defined as all eligible patients who received at least one dose of trial therapy. Patients who do not have an efficacy evaluation will be included and will be classified as unevaluable.

## **8.6. Efficacy Analysis**

### **8.6.1. Primary Efficacy Analysis**

The proportion of successes will be estimated by the number of successes divided by the total number of patients in the efficacy population. Eligible, treated patients who are unevaluable for response will be included in the denominator when estimating the proportion of successes. 95% Confidence intervals for the true success proportion will be calculated according to exact two-stage binomial confidence intervals. (Atkinson and Brown, 1985) Secondary analyses include estimation of the proportion of successes with 95% confidence intervals for each group.

## **8.7. Safety Analysis**

The safety evaluations include AEs, clinical laboratory assessments, vital signs with weight, and physical examination.

The results of this study will be reported using summary tables, figures, and data listings. Continuous variables will be summarized using mean, SD, median, minimum, and maximum. Categorical variables will be summarized by presenting the number (frequency) and percentage in each category.

If any screening safety data is repeated, the measurement taken closest to dosing will be used in the analysis as pre-study baseline. If any post-dose safety data is repeated the measurement taken first at the particular visit in question will be used in the analysis.

### **8.7.1. Demographics and Baseline Characteristics**

Demographic data (e.g. age, gender, race, height, screening body weight, etc.) will be listed for the ITT population. Data will be summarized descriptively (number of patients, mean, SD, median, minimum, and maximum within the efficacy population, overall and by renal impairment group).

Pre-study (i.e., screening and Baseline) data will be listed for the ITT population. When appropriate, tabular summaries of incidence (frequencies) of events/abnormalities or descriptive statistical

summaries (number of patients, mean, SD, median, minimum, and maximum) will be presented within the efficacy population, overall and by renal impairment group.

### **8.7.2. Prior and Concomitant Medications**

The use of prior and concomitant medications taken will be recorded on the CRFs. Prior and concomitant therapies will be coded to a World Health Organization Drug Dictionary (WHO-DD) term. A by-patient listing of prior and concomitant medication use will be included in the CSR.

Prior medications are all doses taken prior to the first dose of study medication. Concomitant medications are all doses taken after the first dose of study medication. If any medications were started prior to dosing and were continued after dosing they will be shown in the listings as prior but will be included in the concomitant summary table.

The use of concomitant medications will be summarized by renal impairment group for the safety population. In each of these summary tables, the number and percentage of patients taking each medication will be presented by ATC Classification.

### **8.7.3. Adverse Events**

Adverse events will be assessed in the safety population.

TEAEs are those that occur after administration of the first study dose until completion of the follow up evaluations. In the case where the start date of the AE is unknown, it will be assumed to be treatment-emergent. Treatment-emergent AEs (TEAEs) will be summarized by system-organ-class (SOC) and preferred term (PT) using the Medical Dictionary for Regulatory Activities (MedDRA®). The frequency of patients who experience TEAEs will be summarized overall cycle. Patients, having the same AE more than once per group, will be counted once for each PT and once within each SOC.

All AEs are listed by patient, including non-treatment-emergent (i.e., pre-dosing or post-dosing) AEs, if applicable. Separate patient data listings are provided for patients who experience treatment-emergent SAEs, TEAEs leading to early termination from the study, or fatal TEAEs.

Additional summary tables will display the number of patients with treatment-emergent AEs by maximum intensity, treatment-emergent AEs by strongest relationship to study drug, and treatment-emergent AEs that led to premature discontinuation of study classified by renal impairment group, system organ class and preferred term. The total number of all treatment-emergent AEs, serious TEAEs, TEAEs by maximum severity, treatment-related TEAEs, TEAEs leading to discontinuations, and TEAEs leading to death will also be summarized by renal impairment group.

CTC Version 4.0 will be used.

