8.3 Lenalidomide Dose Modification Based On Non-Hematological Toxicity (see Table 8.31)

A one-time dose escalation in lenalidomide of one dose level is allowed at any one time point after completion of 2 cycles of treatment if one of the following conditions is met:

1. The patient was originally registered in Group C but has renal function improvement to a point that dialysis is no longer needed; or
2. The patient was originally registered in Group B but has renal function improvement to $\geq 30 \text{ CrCl (mL/min)}$.

All previously established or new toxicities observed any time, are to be managed as per Table 8.31 and Table 8.4.

If drug must be discontinued, the patient comes off treatment and goes to follow-up per Section 4.0 and event monitoring per eCRF completion guidelines. If the toxicity resolves and drug is to be restarted, the dose must be reduced by dose levels as indicated in the dose reduction table.

Please note: Held doses are not made up.

Table 8.31: Dose Modification for Lenalidomide

NCI CTC Toxicity Grade	Day 2-14 of Cycle	≥Day 15 of Cycle
Grade 3 neutropenia associated with fever (temperature $\geq 38.5^{\circ}\text{C}$) or Grade 4 neutropenia	
 Hold lenalidomide. Follow CBC weekly. If neutropenia has resolved to \leqgrade 2, restart at next lower dose level and continue the cycle until day 21. 	
 Hold lenalidomide for remainder of cycle. Restart lenalidomide next cycle (decrease dose by one dose level).
Thrombocytopenia \geq Grade 3 (platelet count $< 50,000/\text{mm}^3$)	
 Hold lenalidomide. Follow CBC weekly. If thrombocytopenia resolves to \leqgrade 2, restart lenalidomide at next lower dose level and continue the cycle through Day 21. 	
 Hold lenalidomide for remainder of cycle. Restart lenalidomide next cycle (decrease dose by one dose level).
Non-blistering rash Grade 3	
 If Grade 3, hold lenalidomide dose. Follow weekly. If the adverse event resolves to \leqgrade 1, restart lenalidomide at next lower dose level and continue the cycle through Day 21. 	
 Hold lenalidomide for remainder of cycle. Restart lenalidomide next cycle (decrease dose by one dose level).

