10.0 Adverse Event (AE) Monitoring and Reporting

Adverse Event (AE) is defined as any new untoward medical occurrence or worsening of a pre-existing medical condition in a patient administered a medicinal product in a clinical investigation and which does not necessarily have a causal relationship with this treatment. An AE can therefore be any unfavorable and unintended sign (e.g., including an abnormal laboratory finding), symptom, or disease temporally associated with the use of a product (investigational or marketed), whether or not considered related to the product (investigational or marketed).

Following written consent to participate in the study, the collection of AEs/SAEs should begin at the initiation of therapy, unless related to a protocol related procedure.

10.1 Toxicity will be scored using CTCAE Version 4.0 for toxicity and adverse event reporting. A copy of the CTCAE Version 4.0 can be downloaded from the CTEP homepage (<http://ctep.info.nih.gov>). All appropriate treatment areas should have access to a copy of the CTCAE Version 4.0. All adverse clinical experiences, whether observed by the investigator or reported by the patient, must be recorded, with details about the duration and intensity of each episode, the action taken with respect to the test drug, and the patient's outcome. The investigator must evaluate each adverse experience for its relationship to the test drug and for its seriousness.

The investigator must appraise all abnormal laboratory results for their clinical significance. If any abnormal laboratory result is considered clinically significant, the investigator must provide details about the action taken with respect to the test drug and about the patient's outcome.

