13.4 Criteria for Patient Withdrawal

Patients may be withdrawn from the study for the following reasons:

- Progressive multiple myeloma
- Patient withdraws consent to continue in the trial
- Patient develops an intercurrent illness that precludes further participation, or requires a prohibited concomitant treatment
- The Investigator withdraws the patient in the patient's best interests
- Patient is lost to follow-up (defined as the inability to contact the patient on 3 separate occasions over a period of 2 weeks)
- Administrative reasons (e.g., the patient is transferred to hospice care)
- An adverse event, which in the opinion of the Investigator, precludes further trial participation
- Pregnancy
- Closure of study by PrECOG

- 13.5 All attempts should be made to complete the End of Study procedures if a patient withdraws from the trial early.
- 13.6 **Phase I:** If a patient fails to complete one cycle of treatment for reasons other than toxicity, the patient will be regarded as inevaluable and will be replaced.
- 13.7 Patients who develop progressive disease while receiving therapy will go to the event-monitoring phase.
- 13.8 Patients who go off protocol treatment for reasons other than PD will go to the event-monitoring phase.
- 13.9 Patients who are in sCR, CR, VGPR, PR, or SD (or usCR, uCR, uVGPR, uPR) may have stem cells harvested at any time after 4 cycles at the discretion of the Investigator. If the patient is continued on therapy, lenalidomide and dexamethasone may be discontinued during the harvest period and the dates of cessation and resumption recorded.

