#### **4.3. Treatment Administration**

Patients must not start protocol treatment prior to registration. Treatment should begin  $\leq$  7 working days of registration.

Dexamethasone will be given at a fixed dose of 40 mg by mouth once weekly on a 28 day treatment cycle. If a dose of dexamethasone is missed, it is up to the treating physician whether the dose should be made up. In addition, continuing dexamethasone if lenalidomide is stopped is also at the discretion of the treating physician.

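### SAP 8.7.3 keys its discontinuation table and listing to leaving the study, not to stopping lenalidomide, so a patient who stops lenalidomide for an adverse event and continues dexamethasone appears in neither

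*SAP*

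**What the plan says.** SAP 8.7.3 refers to discontinuation in three places and defines it in none:

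- a table by system organ class and preferred term of "treatment-emergent AEs that led to premature discontinuation of study classified by renal impairment group";
- a patient listing of "TEAEs leading to early termination from the study";
- an overall summary that includes "TEAEs leading to discontinuations, and TEAEs leading to death will also be summarized by renal impairment group", with neither drug nor study named.

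The protocol treats stopping a drug as a step within the study. Section 8.3 states: "If drug must be discontinued, the patient comes off treatment and goes to follow-up per Section 4.0 and event monitoring". Section 13.8 is similar: "Patients who go off protocol treatment for reasons other than PD will go to the event-monitoring phase". Section 8.0 removes patients who cannot tolerate the lowest dose from the treatment phase only. The two drugs can also end at different times: Protocol 7.11 and 7.12, repeated in SAP 4.3, say that "continuing dexamethasone if lenalidomide is stopped is also at the discretion of the treating physician".

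For each adverse event, Protocol 10.1 requires a record of "the action taken with respect to the test drug". The text of SAP 8.7.3 uses that item in no output.

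**The concern.** The trial sets the dose of lenalidomide. Under Protocol 7.23 only Cycle 1 dose-limiting toxicities define the MTD, while treatment runs until progression, intolerable toxicity or refusal. How often patients later have to give up lenalidomide for an adverse event is therefore a direct measure of whether the chosen dose can be sustained. The safety profile is a secondary objective in both documents (Protocol 2.22, SAP 3.2).

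A table keyed to leaving the study answers a different question. It can show few discontinuations while patients are stopping lenalidomide for toxicity. With three undefined phrases in one section, two programmers could also produce different counts from the same data.

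**Working it through.** The plan states no figure to reproduce, so the check sets the passages side by side and follows each kind of patient through them.

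**Two possible readings of the SAP phrase**

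- *Literal:* the adverse event ended all participation, follow-up included.
- *Off protocol treatment:* the adverse event ended protocol therapy, whether or not follow-up goes on.

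The protocol's vocabulary leans to the second. Section 13.4 lists progression and adverse events as reasons for withdrawal from the study, yet 13.7 and 13.8 send such patients to event monitoring. Footnote 18 of the test schedule uses the terms off-study and discontinued for patients from whom progression or survival data are still wanted. In SAP 8.4.2, time to treatment failure for a patient taken off study as a non-protocol failure is censored at removal from treatment.

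**Who appears in the table and listing**

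| Patient with an adverse event | Literal | Off protocol treatment | Keyed to lenalidomide |
|---|---|---|---|
| Stops both drugs and leaves follow-up | counted | counted | counted |
| Stops both drugs, moves to event monitoring | missed | counted | counted |
| Stops lenalidomide, continues dexamethasone | missed | missed | counted |

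The third row is missed on both readings. If that patient later stops dexamethasone for progression, the recorded reason for coming off treatment is progression, and the toxicity stop of lenalidomide still does not appear.

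**Whether another output covers the third row**

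- The summary count of discontinuations might, if it is programmed as drug discontinuation. The SAP does not say so, and the count is not broken down by event term.
- Time to treatment failure (SAP 8.4.2) counts removal from treatment for adverse events, but pools it with progression and refusal and does not separate the drugs.
- Protocol 16.37 plans a per-agent summary of treatment duration and dose. It is absent from the SAP text, although SAP 9 declares no changes. It would describe exposure, not the reason for stopping.

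**Denominator**

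SAP 8.7.3 uses the safety population, which SAP 8.5.2 defines as everyone given at least one dose. From the counts in SAP 8.1:

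- Group A: 15 + 15 = 30 expected, 18 + 15 = 33 maximum.
- Groups B and C, each: 18 + 15 = 33 expected, 24 + 15 = 39 maximum.
- Total: 30 + 33 + 33 = 96 expected, 33 + 39 + 39 = 111 maximum, before any Phase I replacements.

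One uncounted patient therefore changes a group's proportion by between 1/39 = 2.6 and 1/30 = 3.3 percentage points, and the overall proportion by between 1/111 = 0.9 and 1/96 = 1.0 points. The documents give no rate of lenalidomide stops for toxicity and no proportion continuing dexamethasone, so the number of such patients cannot be derived.

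**The case against.** The strongest reply is that this is loose wording and not a gap. The protocol uses study withdrawal for patients who are only off treatment, so the SAP phrase naturally means off treatment because of an adverse event. Protocol 8.3 takes a patient off treatment when drug must be discontinued, and Table 8.31 sends lenalidomide discontinuations to follow-up. On that view lenalidomide-only stops should be few. Detailed output definitions are also in a separate template that is not available here and may settle the matter.

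Much of this stands. A reader might infer from the SAP wording that toxicity stops are largely missed, or would be reported as zero. The documents do not support that: it needs the literal reading, which the protocol's usage does not follow, and it overlooks the unqualified count of discontinuations. A reader might also take Table 8.42 to show that lenalidomide goes on after dexamethasone ends. The table says only that dexamethasone is discontinued and is silent on lenalidomide. Finally, the 63 patients treated at the MTD are the wrong denominator, since they form the efficacy population.

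What the reply does not remove is the third row of the table. Protocol 7.11 and 7.12 and SAP 4.3 expressly allow dexamethasone to continue, which does not sit easily with 8.3. While both statements stand, a patient who has stopped only lenalidomide need not count as off treatment.

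**Conclusion.** The concern holds in a limited form. SAP 8.7.3 does not define discontinuation, and its table and listing name the study and not the drug. On either reading they omit a patient who stops lenalidomide for an adverse event and continues dexamethasone, so they can under-count toxicity stops of the drug whose dose the trial sets. On the literal reading they also omit patients who stop both drugs and move to follow-up, but that reading is the less likely one.

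The extent is unknown. It depends on how often dexamethasone is continued alone and on how the sites resolve Protocol 8.3 against 7.11 and 7.12. The conclusion assumes that the separate output templates do not already define the category by drug. The point should be corrected, but it does not affect the primary efficacy analysis.

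**What to change.** 1. In SAP 8.7.3, key the table by organ class and term, the listing and the summary line to treatment-emergent events leading to permanent discontinuation of lenalidomide, by renal group, using the action taken on the test drug under Protocol 10.1.
2. Show discontinuation of dexamethasone, and of both drugs, where the eCRF or dosing records allow.
3. Keep withdrawal from the study for an adverse event as its own line.
4. Confirm that the eCRF captures the action separately for each drug. Protocol 10.1 refers to the test drug in the singular, and the items that 10.21 requires for every adverse event do not include action taken.
5. Reconcile Protocol 8.3 with 7.11 and 7.12, and align SAP 4.3, because together they decide who counts as off treatment. Which rule should apply is for the study team.

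Tables of holds and dose reductions would be useful but are optional.

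The cost is SAP wording, a few table rows and the eCRF check. Reported discontinuation counts may be higher as a result. If the action was not captured per drug, the dexamethasone and both-drug lines would have to come from dosing records or be dropped.

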10.11 Assessment of Attribution

When assessing whether an adverse event is related to a medical treatment or procedure, the following attribution categories are utilized:

Definite: The adverse event *is clearly related* to the investigational agent(s).
Probable: The adverse event *is likely related* to the investigational agent(s).
Possible: The adverse event *may be related* to the investigational agent(s).
Unlikely: The adverse event *is doubtfully related* to the investigational agent(s).
Unrelated: The adverse event *is clearly NOT related* to the investigational agent(s).

10.12 When a study includes both investigational and commercial agents, the following apply:

- When an investigational agent(s) is used in combination with a commercial agent(s), the combination is considered investigational. Reporting of adverse events follows the guidelines for investigational agents.

10.2 All Adverse Events are to be graded at each evaluation and all pretreatment symptoms/conditions are to be evaluated at baseline per Common Terminology Criteria for Adverse Events (CTCAE) Version 4.0 grading. The specific Adverse Events/Symptoms in the table below are to be collected as indicated below:

Category	Adverse Event/Symptoms	Baseline	Each Evaluation
Blood/Bone Marrow	Hemoglobin	X	X
	Neutrophils/Granulocytes (ANC/AGC)	X	X
	Platelets	X	X
Constitutional Symptoms	Fatigue (lethargy, malaise, asthenia)	X	X
Neurology	Neuropathy-Sensory	X	X
Dermatology/Skin	Rash/Desquamation	X	X
Renal/Genitourinary	Cystitis	X	X
Lymphatics	Edema: Limb	X	X
Gastrointestinal	Nausea	X	X
	Vomiting	X	X
	# of stools per day	X	
	Diarrhea		X
Musculoskeletal/Soft Tissue	Muscle Weakness/Lower Extremity	X	X

10.21 Submit via appropriate electronic Case Report Forms (eCRFs) the following AEs experienced by a patient and not specified in Section 10.2. If known, the diagnosis of the underlying illness or disorder should be recorded, rather than individual symptoms. The following information should be documented for all AEs: date of onset and resolution, severity of the event; the investigator's opinion of the relationship to investigational product; treatment required for the AE; cause of the event (if known); and information regarding resolution/outcome.

- Grade 1 and 2 AEs deemed *possibly, probably, or definitely* related to the study treatment or procedure.
- Grade 3 and 4 AEs regardless of attribution to the study treatment or procedure
- Grade 5 AEs (Deaths)

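### SAP 8.7.3 tabulates all adverse events, but protocol 10.21 admits non-serious, unsolicited Grade 1-2 events to the eCRF only if judged related, so all-cause, low-grade and unrelated figures come out low

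*SAP*

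**What the plan says.** SAP 8.7.3 summarises by renal impairment group "The total number of all treatment-emergent AEs, serious TEAEs, TEAEs by maximum severity, treatment-related TEAEs, TEAEs leading to discontinuations", and those leading to death. It also tabulates the number of patients with events by maximum intensity and "treatment-emergent AEs by strongest relationship to study drug". The treatment-emergent window runs from the first dose to the end of the follow-up evaluations. SAP section 9 plans no changes from the protocol, and the SAP text nowhere mentions a limit on which events are collected.

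Protocol 10.2 has a table of solicited events: "The specific Adverse Events/Symptoms in the table below are to be collected as indicated below". It carries no attribution filter. For everything else, protocol 10.21 says: "Submit via appropriate electronic Case Report Forms (eCRFs) the following AEs experienced by a patient and not specified in Section 10.2". The classes that follow are:

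- "Grade 1 and 2 AEs deemed *possibly, probably, or definitely* related to the study treatment or procedure"
- events of Grade 3 or 4, whatever their cause
- deaths, regardless of attribution up to 30 days after the last treatment or procedure, and after that only if at least possibly treatment related.

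Protocol 10.1 is broader: "All adverse clinical experiences, whether observed by the investigator or reported by the patient, must be recorded". It does not mention the eCRF. Protocol 10.41 requires any SAE to be reported, without limit of grade or attribution, up to 30 days after the last dose, and later SAEs only if judged at least possibly related.

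**The concern.** One class of event falls through: Grade 1-2, non-serious, not on the 10.2 list, and judged unrelated to treatment or procedure. Under 10.21 it is not submitted, yet the SAP tables are headed as totals of all events and split by relationship. For unsolicited, non-serious mild events, an almost empty unrelated row would reflect the collection rule and not what patients experienced.

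The safety profile is a secondary objective (protocol 2.22). In patients with renal failure, telling drug effects from background illness is a large part of that objective. Protocol 16.21 and 16.22 set all adverse events beside related toxicities, and at low grade the filter removes part of that contrast. The tables are also split by renal group. If the groups differ in background mild illness, the filter removes a different share from each.

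**Working it through.** The plan gives no figure to reproduce here, so the first step sets the collection rules against the outputs.

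| Event class | Route into the data | Attribution filter |
|---|---|---|
| Solicited items, any grade | 10.2 table | None |
| Unsolicited Grade 1-2, non-serious | 10.21 | Only if related to treatment or procedure |
| Unsolicited Grade 3-4 | 10.21 | None |
| SAE of any grade, up to 30 days after last dose | 10.41 | None |
| Death, up to 30 days after last treatment | 10.21 | None |
| Later death or SAE | 10.21, 10.41 | Only if at least possibly related |

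**Effect on the SAP outputs**

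- *Total of all events:* too low by the number of filtered events.
- *Maximum intensity:* a patient whose only event of a given term was mild and filtered drops out, so the Grade 1 and Grade 2 rows taken together are too low.
- *Strongest relationship:* the unrelated rows are too low. The related rows stand, because a related event always passes the filter and always outranks an unrelated one in the same patient.
- *Percentage of patients with a related event:* unchanged. SAP section 10 uses the whole group as the default denominator, and the numerator is complete with respect to this filter.

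**Direction and size of the event-level effect**

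Let f be the share of all events that are unsolicited, non-serious and Grade 1-2, r the related share among those, and q the related share among events captured whatever their attribution. Then:

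- captured fraction = 1 − f(1 − r)
- true related share = f·r + (1 − f)·q
- observed related share = true related share ÷ captured fraction

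The observed share exceeds the true share whenever r is below 1 (with f and the true share above zero), and equals it when r = 1. The direction is therefore fixed. The size is not, because the documents give no adverse event rates. With assumed values only:

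| f | r | q | Captured | True related share | Observed related share |
|---|---|---|---|---|---|
| 0.2 | 0.8 | 0.4 | 1 − 0.2×0.2 = 96% | 0.16 + 0.32 = 48% | 0.48/0.96 = 50% |
| 0.4 | 0.5 | 0.4 | 1 − 0.4×0.5 = 80% | 0.20 + 0.24 = 44% | 0.44/0.80 = 55% |
| 0.6 | 0.2 | 0.4 | 1 − 0.6×0.8 = 52% | 0.12 + 0.16 = 28% | 0.28/0.52 = 54% |

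Over f from 0.2 to 0.6 and r from 0.2 to 0.8, capture runs from 52% to 96%. On the renal group split, with r = 0.5, a group with f = 0.2 would have 90% captured and one with f = 0.6 would have 70%.

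**The case against.** **Selective low-grade collection is a legitimate choice.** Agreed. The point is about tables headed as all events, not about the collection rule.

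**Protocol 10.1 requires everything to be recorded.** It can be read as source recording, with 10.21 governing eCRF submission, so the two need not conflict. Footnote 11 of the Test Schedule also calls the 10.2 list a minimum. If sites entered more than 10.21 asks, the gap shrinks, but capture could then vary by site. The eCRF instructions and the table templates are separate documents, and a footnote may exist there. What can be said is that the SAP text carries none.

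**The reach is modest.** This stands. Four of the five likely risks in protocol 15.16 (neutropenia, thrombocytopenia, fatigue, diarrhea) are covered by the solicited list. Dose-limiting toxicities and the stopping rule rest on related events of Grade 3 or higher, so neither changes.

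**Three stronger readings that the documents do not support**

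- A reader might infer that every unsolicited mild event in the data is drug-related by construction. It is not. The filter also admits events related only to a procedure, and SAEs of any grade come in whatever their attribution.
- A reader might infer that the percentage of patients with a related event is inflated. With the whole group as denominator it is not; only ratios of related to all events are.
- A reader might infer that Grade 3 or higher is complete throughout. Later deaths and SAEs are subject to an attribution filter while the SAP window stays open to the end of follow-up, so a table limited to severe events also needs a time limit.

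**A footnote would be enough.** It is the least that is needed, but it would leave totals that mix complete and filtered classes, which a reader cannot separate.

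**Conclusion.** The mismatch is real and narrow. If sites follow 10.21 as written, and if any non-serious, unsolicited Grade 1-2 event is judged unrelated, then all-cause any-grade counts, the low-grade rows and the unrelated rows are understated, and any ratio of related to all events is overstated. The percentage of patients with a related event, Grade 3-4 events, SAEs within 30 days of last dose and the solicited 10.2 items are not affected. This takes it that SAE reports are brought into the safety dataset, as the planned SAE summaries imply. The size of the bias cannot be derived from the documents; the 52% to 96% range rests wholly on assumed inputs. The trial has a single treatment regimen and descriptive safety summaries, so no formal test is touched. What is at stake is how the safety tables are read.

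**What to change.** In SAP 8.7.3:

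1. State the protocol 10.21 collection rule.
2. Limit the all-cause totals and the maximum-severity and relationship tables to classes collected regardless of attribution: Grade 3 or higher events, SAEs of any grade, and the 10.2 items. Count deaths and SAEs only up to 30 days after last dose.
3. Show non-serious, unsolicited Grade 1-2 events in a separate table titled *related to study treatment or procedure only*.
4. List later deaths and SAEs as related only. Second primary malignancies are an exception, since protocol 10.5 requires them to be reported whatever their relationship. For other late events, take the cut-off from the eCRF manual that protocol 10.22 refers to.

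In the protocol, reconcile 10.1 with 10.21 by saying which events are recorded in source only and which are entered in the eCRF.

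The cost is SAP wording, table titles and table layout, with no new data. The downside is that the all-cause tables no longer include related mild unsolicited events, which appear in their own table.
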